Official Title of the study: ADDRESS: Activity Dependent Rehabilitation via Transcutaneous Electrical Spinal Stimulation to Restore Upper Extremity Functions in Spinal Cord Injury

NCT number: NCT03184792

Date of the document: February 22, 2022

Statistical Analysis Plan:

For comparison of the functional changes occurring during each intervention phase, one-way repeated measures ANOVA will be used with post-hoc pairwise analysis as per Tukey LSD test (IBM SPSS version 26). A Shapiro-Wilk Test will be used to determine whether repeated measurements follow a normal distribution. Mauchly's test will be used to analyze the assumption of sphericity, and degrees of freedom will be corrected using Greenhouse-Geisser estimates of sphericity when the assumption is violated. We will directly compare the benefits of training alone and stimulation combined with training by calculating the cumulative changes in each outcome measure across the two intervention arms. These values will be normalized to baseline to control for individual variation in function at the beginning of the study and compared between the training and stimulation + training interventions using a paired-samples T-test.

Additionally, score changes relative to the preceding treatment block will be calculated to compare the improvement rates between intervention phases repeated monthly. For all tests, $p < 0.05$ will be considered significant. All participants' data will be included in all analyses. Given the early stage of research and the lack of prior data on transcutaneous spinal cord stimulation for restoring upper limb function, power analysis and sample size calculations are not feasible.

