After Phase I, patients will be randomized to receive either physical therapy alone (Arm A) or physical therapy plus transcutaneous spinal cord stimulation (Arm B) for 6 weeks. Then, patients will be followed up for an 8-week wash-out period, during which neither study intervention will be administered. During wash-out period, patients will not be allowed to receive treatments that violate exclusion criteria (e.g., botulinum toxin injections or tendon/nerve transfer

surgery in the upper extremity) or new treatments that could affect the study's outcome (e.g., alternative exercise therapies or robotic rehabilitation targeting upper extremity function).

However, they can continue to get their regular lower extremity physiotherapy.

Next, the intervention arms will be crossed over, i.e., patients who received the A intervention arm first will receive the B intervention arm, and vice versa, for another 6 weeks. In each intervention arm, sessions will last 2 hours/day, 2-5 days/week.

Transcutaneous Spinal Cord Stimulation Procedure: Transcutaneous spinal electrical stimulation is a non-invasive neurostimulation technique. Stimulation will be delivered through the skin using surface hydrogel electrodes, which are commonly used in practice today.

During the first stimulation session, optimal electrode placement and stimulation parameters will be determined using hand function testing and electromyographic (EMG) testing of the upper extremity muscles. Hand function will be tested by the abbreviated GRASSP test, Quantitative Prehension subscale, pinch and grip force measurements, and Capabilities of Upper Extremity Test (Cue-T). EMG testing will be done using skin surface recording electrodes.

Transcutaneous spinal stimulation paradigms that elicit appropriate muscle activation with the lowest threshold stimulation current will be identified. A painless cutaneous enabling motor control paradigm will be used for this purpose: biphasic or monophasic rectangular pulses of 1.0 ms per phase duration will be delivered at a frequency of approximately 30 times per second (Hz). Within these pulses, a very high carrier frequency of 10 kHz is delivered to avoid painful sensations as the current crosses the skin (i.e., the Russian Method of muscle stimulation). Stimulation intensity will range from 1 to 180 mA. During the initial testing, stimulation will be delivered for a duration of 10 to 30 seconds.

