After determining the optimal initial stimulation configuration, we will deliver physical therapy sessions while transcutaneous spinal stimulation is administered for a total of up to 90 minutes. The duration of 90-minute stimulation is determined based on the effect mechanism and safety information reported in earlier clinical studies with spinal stimulation. Time without stimulation will be interspersed to examine the difference in movement with and without stimulation.

Hand and Arm Physical/Occupational Therapy Protocol: The therapy program will include progressive functional task practice for upper extremity motor training (i.e., active assistive range of motion, stretching, strengthening, reaching and grasping exercises, and fine motor skills training). The physical therapy program will be tailored to the patient's specific functional deficits and needs.

For safety monitoring, we will document vital signs (blood pressure, pulse, respirations, temperature), orientation to time and place, and skin examination before and at the end of each

session. For cardiovascular safety, non-invasive continuous blood pressure monitoring will be done during transcutaneous cervical spinal electrical stimulation. Patients will be encouraged to report any abnormal feelings and discomfort throughout the session. After each session, patients will be released if they are deemed stable. If not, they will be referred to a healthcare professional for evaluation and provided appropriate care.

Every two weeks throughout the intervention, we will measure and document the functional improvements observed during stimulation and those that persist beyond the stimulation. At the end of each intervention arm and wash-out period, outcome measurements will be repeated, as described in the study design figure above.

Phase III – Follow-up

After completing the two-arm crossover intervention phase (Phase II), patients will be provided with a home rehabilitation exercise program. Three follow-up visits during the early follow-up period (8 weeks following the last intervention session) and one last follow-up visit at the end of one year of the study will be scheduled, where assessments and measurements will be done as described in the study design figure above, at UW Rehabilitation Department and/or in Amplifying Movement & Performance Laboratory.

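### The post-hoc rule Tukey LSD names no single procedure; run as LSD, it leaves the visit-pair tests unadjusted, and the familywise error depends on a visit count and an F-test gate that the SAP does not state

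*SAP*

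**What the plan says.** The first paragraph of the SAP analyses change over time in each outcome as follows: "one-way repeated measures ANOVA will be used with post-hoc pairwise analysis as per Tukey LSD test". The second paragraph sets the level: "For all tests, $p < 0.05$ will be considered significant". No other multiplicity adjustment is described. The SAP does not say which time points enter the ANOVA, or whether pairwise tests are run only after a significant F test.

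Sphericity is tested, and "degrees of freedom will be corrected using Greenhouse-Geisser estimates of sphericity when the assumption is violated". That correction applies to the F test, not to the pairwise comparisons.

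The protocol's Phase II section gives the schedule. Each arm runs for a fixed period ("physical therapy plus transcutaneous spinal cord stimulation (Arm B) for 6 weeks"), with repeated measurement inside it: "Every two weeks throughout the intervention, we will measure and document the functional improvements observed during stimulation". It adds: "At the end of each intervention arm and wash-out period, outcome measurements will be repeated". Phase III adds further assessments: "Three follow-up visits during the early follow-up period", plus one at one year. The full visit grid is in a design figure that is not available here.

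The comparison of training with stimulation plus training is a separate paired t-test on cumulative change.

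**The concern.** Tukey's test and the LSD test are different procedures. HSD controls the chance of any false difference across all pairs of means. LSD is a set of ordinary pairwise t-tests at the nominal level, whose only protection is a preceding significant F test, if one is required. Two analysts following this sentence could produce different p-values from the same data, and the choice could be made after the results are seen.

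The pairwise tests are what would support statements about when improvement first appears, whether it is still growing late in a period, and whether it persists. One of the protocol's primary objectives concerns immediate and lasting improvement, so such statements are likely to be made. If several are drawn from one unadjusted set, the chance that at least one is false can be well above 5%.

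**Working it through.** The plan gives no familywise figure to reproduce; 0.05 per test is its only stated level.

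**Inputs.**
- Level: 0.05 for every test (SAP).
- Visits per period: 6 weeks with measurement every 2 weeks gives weeks 0, 2, 4 and 6, so k = 4. This assumes a week-0 measure. Two periods in one ANOVA would give k = 8.
- The number of levels actually used is not stated, so a range of 3 to 8 is shown.
- Sample size is not stated; n = 6, 10 and 20 are assumed.

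**Number of pairs.** m = k(k − 1)/2, so k = 3, 4, 5, 8 give m = 3, 6, 10, 28.

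**Large-sample formula, no gate, no true change.** The chance of at least one pair beyond the 5% t limit is the upper tail of the studentized range of k means at 1.96 × √2. This gives 12.2% (k = 3), 20.3% (k = 4), 28.6% (k = 5) and 50.9% (k = 8). Treating the pairs as independent, 1 − 0.95^m, gives 14.3%, 26.5%, 40.1% and 76.2%. That is too high, because pairs that share a visit are correlated.

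**Simulation.** Unadjusted paired t-tests, 20,000 runs per setting, n = 6, 10 and 20, compound symmetry 0.5 and AR(1) 0.8. Chance of at least one false pair:

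| Visits | No gate, no true change | F gate, no true change | F gate, one visit differs greatly |
|---|---|---|---|
| 3 | 12–13% | about 5% or less | 5% |
| 4 | 20–23% | about 5% or less | 12–13% |
| 5 | 27–32% | about 5% or less | 19–23% |
| 8 | 46–61% | about 5% or less | 41–52% |

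The last column follows from the first. If one visit differs greatly, the F test is almost always significant, and the other k − 1 visits are then compared without adjustment. With k = 4, the three equal visits give the 3-visit ungated rate, 12.2% by the formula.

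**Dependence on the true pattern, with gate and large true changes.**
- 4 visits, gains to week 4 and then a plateau: only weeks 4 and 6 are equal, one null pair, 5%.
- 4 visits, a single step at week 4: two separate null pairs, 1 − 0.95² = 9.75%; simulated 9–10%.
- 4 visits, one visit differs and three are equal: 12–13%.
- 8 visits, the same gains in each period with return to baseline after wash-out: four separate null pairs, 1 − 0.95⁴ = 18.5%; simulated 18–19% with independent residuals.

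**Per-pair error.** In these patterns each truly null pair was rejected about 5% of the time; with the gate and no true change, less often.

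**After the fix.** Holm-adjusted paired t-tests kept the familywise rate at about 5% or less in every setting checked.

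**The case against.** The strongest defence is that post-hoc testing after an ANOVA is naturally read as conditional on a significant F, and then LSD is not badly behaved. It holds about 5% when nothing changes, and about 5% in all cases if only three levels are compared. The SAP's wording could mean visits within a period or the intervention phases themselves, and the latter might be three levels. This stands, and it is why no single inflated rate can be attached to the plan. It does not rescue the label: the gate is not written down, the levels are not listed, and the two-weekly schedule points to at least four visits per period.

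If HSD was meant, the LSD inflation does not arise. But HSD with a pooled error term relies on sphericity, and the Greenhouse-Geisser step does not reach the pairwise tests. A reader might go further and infer that the SAP expects sphericity to fail. It does not say so; its correction is conditional on a violation.

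A reader might also infer that any one statement, such as improvement by week 2, is false far more often than 5%. That is not supported. The error for each null pair stays at about 5% or less, and the SAP's 0.05 is a per-test level. What rises is the chance of at least one false pair in the set.

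Finally, the affected results describe time course in what the SAP calls early-stage research, and the direct treatment comparison does not use this rule. That stands and limits the severity.

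**Conclusion.** The point holds in a limited form. The SAP names a post-hoc procedure that does not exist as one method, and nothing else in it controls error over pairs of visits. This should be fixed, but it does not undermine the treatment comparison.

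On the most natural reading of the schedule (four visits in a period, which assumes a week-0 measure), LSD gives a within-outcome familywise error of about 20–23% ungated with no true change. Gated, it gives about 5–13% when some visits truly differ. Some real change is plausible, because both arms receive progressive task practice.

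A reader might take the range from about 13% to 50% as the error rate of LSD in this trial without conditions. The documents do not support that. The upper end needs eight visits in one ANOVA, and either no gate or seven of the eight visits truly equal. The SAP does not specify an eight-level ANOVA, and seven equal visits is an unlikely pattern over two 6-week therapy periods. All figures rest on assumed visit counts, sample sizes and correlation structures.

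**What to change.** Replace the post-hoc clause with wording such as: *For each outcome, visits [listed] will be compared by paired t-tests, each with its own error term, with p-values Holm-adjusted over all listed pairs within that outcome; no preceding significant F test is required.* Separate error terms remove the sphericity assumption from these comparisons. The Greenhouse-Geisser step can stay for the F test. Holm is one valid choice among several; what matters is to name one procedure, list the visits and state whether a gate applies.

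To save power, the family can be limited to start-of-arm against weeks 2, 4 and 6. In that case either make no claim about week 4 against week 6, or add that contrast to the Holm family. The smallest p-value must then fall below 0.05/3 = 0.0167 with three contrasts or 0.05/4 = 0.0125 with four, against 0.05/6 = 0.0083 for all six pairs of four visits.

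The cost is one sentence in the SAP and no new data or visits. Some post-hoc p-values become larger, which is a real loss of power if the sample is small.

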Recently, a non-invasive technique for spinal stimulation, specifically transcutaneous electrical spinal cord stimulation, has been demonstrated to be effective in improving motor function in both healthy individuals and patients with spinal cord injuries. The effects of this novel technology on upper extremity motor function have not been tested. This research study employs a prospective, experimental, randomized crossover design to assess the safety and efficacy of transcutaneous cervical electrical stimulation in improving upper limb function in patients with cervical spinal cord injury.

Electrical cervical stimulation has been shown to be effective in improving upper limb function in animal studies conducted in our laboratory. By other groups, transcutaneous electrical spinal

cord stimulation has been demonstrated to be effective in improving lower extremity motor function in both healthy individuals and patients with spinal cord injury. Transcutaneous spinal stimulation was applied to the skin via external electrodes placed midline on the spinous processes of the vertebrae. A novel, well-tolerated, and painless transcutaneous electrical enabling motor control strategy was used for neuromodulation. Previously, no adverse effects have been reported with transcutaneous electrical spinal cord stimulation. Patients described a non-disturbing tingling sensation beneath the electrodes.

The purpose of the study is to implement and test transcutaneous spinal stimulation in patients with cervical spinal cord injury (traumatic or degenerative etiology) in combination with a rehabilitation program. We aim to enhance both arm and hand sensorimotor functions.

Our primary objectives are:

1. To establish a novel, non-invasive therapeutic stimulation approach in patients with cervical spinal cord injury.
2. To determine transcutaneous stimulation locations and parameters that are safe and effective for augmenting hand motor and sensory function.
3. To evaluate both immediate and lasting improvements in hand motor and sensory function via transcutaneous cervical spinal stimulation.

Our secondary objectives are to document and analyze other potential benefits of electrical neuromodulation, including a decrease in spasticity, an increase in bowel and bladder control, and an improvement in mobility.

Inclusion Criteria. Individuals who

1. has cervical (C7 or higher) spinal cord injury with a duration of at least 1 year duration

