18. are unable to read and/or comprehend the consent form.
19. lack of ability to fully comprehend and/or perform study procedures in the investigator's opinion/judgement
20. has a history of severe allergy (i.e., allergic reaction that could not be treated with antihistaminic medication

will be excluded.

[figure not shown]
If a patient inquires about the study, they will then be provided an opportunity to speak with research assistants about the study. This will be done in a quiet and private area, such as a patient's room or office, in order to maintain confidentiality. If the patient contacts us via phone, research assistants will provide information about the study and answer their questions.

Research assistants will explain that participation in the study is strictly voluntary, and if the patient chooses not to enroll, their care will not be affected in any way. The research team member obtaining informed consent will explain that participation in the experiment is not required nor connected with the clinical treatment or procedure. No individual incentives will be offered in exchange for participation in the study.

Subjects who meet all the inclusion criteria and none of the exclusion criteria at their pre-screening and initial evaluation visit will be approached by research assistants. (S)he will explain the study and review the consent with the patient. Patients will be assured that participation is voluntary and that they will continue to receive their usual clinical care if they choose not to participate. Subjects will be given 1 week to decide whether they wish to participate in the study.

We will use advertisement flyers/information sheets that will be clearly displayed in the neurosurgery and rehabilitation outpatient departments for all to see. Additionally, subjects will be informed about the study during their routine control visits in the Departments of Neurosurgery and Rehabilitation Medicine by their primary physicians. Notifications may be posted on our departmental and laboratory websites and distributed via listservs that reach this community.

Study design:

Week 1 2 3 4 5

Timeline for outcome measurements:
Weeks without asterisk – only GRASSP quantitative prehension and grip & pinch strength measurements will be done

A Physical Therapy Only

A – Physical Therapy Only

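### The main comparison of stimulation plus training with training is a plain paired t-test with no period term and no stated start visit for the second arm, and no analysis of wash-out or follow-up data is named

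*SAP*

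**What the plan says.** The SAP's first paragraph sets out the only direct comparison of the two interventions. It rests on "calculating the cumulative changes in each outcome measure across the two intervention arms". The values are then "normalized to baseline to control for individual variation in function at the beginning of the study" and compared by a paired-samples t-test. No period, sequence or carry-over term appears. The second paragraph adds a separate comparison in which "score changes relative to the preceding treatment block will be calculated to compare the improvement rates between intervention phases".

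In the protocol, Phase II gives each patient both interventions for 6 weeks each, in randomised order, with 8 weeks of wash-out between them. The allocation ratio is not stated. Every two weeks the team records "the functional improvements observed during stimulation and those that persist beyond the stimulation". The protocol also states: "At the end of each intervention arm and wash-out period, outcome measurements will be repeated". Phase III schedules three early follow-up visits and one at the end of one year. Primary objective 3 is "To evaluate both immediate and lasting improvements in hand motor and sensory function via transcutaneous cervical spinal stimulation". The SAP mentions neither wash-out nor follow-up.

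**The concern.** Three choices are left to the analyst.

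- **Start visit.** The second arm's change could be counted from study baseline or from the end of wash-out. The two agree only if nothing of the first-arm gain remains after 8 weeks. The protocol's rationale and objective 3 both hope that something does.
- **Score.** On- and off-stimulation improvements are both recorded, and the SAP does not say which enters the test.
- **Period.** Recovery, practice or learning may make arm 2 gains differ from arm 1 gains. If the sequences end up unequal, a plain paired test carries part of that difference into the treatment estimate.

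The second gap concerns objective 3. *Lasting* may mean improvement that remains once stimulation is switched off within an arm, or benefit that outlasts the course of treatment. For the second meaning, the end of wash-out is the last scheduled assessment at which the randomised groups have had only one intervention each. The SAP makes no stated use of it.

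**Working it through.** **Inputs.** The documents give no effect size, SD, sample size or retention figure, so there is no planned figure to reproduce and every value below is an assumption. The scale is raw change, before the SAP's normalisation.

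- a = gain from training; b = a + t = gain from stimulation plus training; t = true difference
- L = share of first-arm gain left after wash-out; M = share left at the end of arm 2
- c = loss of arm 2 gain per unit of residual gain
- P = period effect on arm 2 gain; p = share of patients who get training alone first (A-first)

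**Study-baseline start** (stimulation plus training minus training)

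- A-first: (Ma + b − cLa + P) − a = t + (M − cL)a + P
- B-first: b − (Mb + a − cLb + P) = t − (M − cL)b − P
- Mean: t + (M − cL)(pa − (1−p)b) + (2p−1)P

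**Pre-arm start** (end of wash-out for arm 2, so the residue L is subtracted)

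- A-first: t − (cL + L − M)a + P
- B-first: t + (cL + L − M)b − P
- Mean: t + (cL + L − M)((1−p)b − pa) + (2p−1)P

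At 1:1, pa − (1−p)b = −t/2 and the period term vanishes. The means become t[1 − (M − cL)/2] and t[1 + (cL + L − M)/2].

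**Results at 1:1, L = 0.5**

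| Scenario | Study baseline | Pre-arm |
|---|---|---|
| Stable residue: M = 0.5, c = 0 | 0.75t | 1.00t |
| Residue limits arm 2 gain: M = 0.5, c = 0.5 | 0.875t | 1.125t |
| Residue fades: M = 0.25, c = 0 | 0.875t | 1.125t |
| Full offset: M = 0.5, c = 1 | 1.00t | 1.25t |

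In the stable case the study-baseline mean is t(1 − L/2), which is 0.875t at L = 0.25 and 0.50t at L = 1.

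**Unequal sequences.** Take a = t, so b = 2t, in the stable case with L = 0.5 and P = 0. Study baseline gives t + 0.5(0.4t − 1.2t) = 0.60t at 4:6 (A-first:B-first) and t + 0.5(0.6t − 0.8t) = 0.90t at 6:4. Pre-arm stays at t. Now add P = 0.5t. The period term is (2p−1)P = −0.1t at 4:6 and +0.1t at 6:4, so pre-arm gives 0.90t and 1.10t. Averaging the two sequence means with equal weight sets that term to zero and returns 1.00t.

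**Power.** Assume N = 10 at 5:5, a = t = 1, SD of the paired difference 1 within sequence, and a stable residue. A plain paired test has about 80% power on the pre-arm start. On the study-baseline start at L = 0.5 the sequence means are 1.5 and 0.0. The average falls to 0.75 and the plain test counts the gap as noise, adding variance 0.25 × 1.5² ≈ 0.56. Simulated power is about 36%. This compares the two starts only under the conditions that favour the pre-arm start.

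**Score.** If stimulation adds an immediate effect s that ends at switch-off, on-stimulation scores estimate t + s and off-stimulation scores estimate t.

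**Precision at the end of wash-out.** The unadjusted 95% half-width is t(0.975, n−2) × √(1/nA + 1/nB). At 5 per sequence it is 2.306 × 0.632 = 1.46 SD; at 10 per sequence it is 2.101 × 0.447 = 0.94 SD.

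**The case against.** The strongest reply is that context already points to within-arm change. The SAP opens with changes during each intervention phase, the additional comparison uses the preceding treatment block, and normalising to baseline reads naturally as scaling. That is fair, and it makes the pre-arm start the likelier intention. It does not settle the matter. The block comparison is a separate analysis and does not say whether its reference is the end of the block or the end of wash-out.

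A reader might infer that the SAP does count the second arm from study baseline and so biases its main result. The documents do not say that. A reader might also infer that a pre-arm start is always the better choice. The table shows otherwise: when the residue fades or limits further gain, the pre-arm start can overstate the effect by as much as study baseline understates it, or by more.

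Nor is a spurious benefit shown at equal sequences. At 1:1 with t = 0 and P = 0, both starts average zero. The harm shown there is distortion of a real effect and lost power.

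Finally, objective 3 says only that improvements will be evaluated, and *lasting* may mean off-stimulation benefit within an arm. It cannot be said that the plan breaks a promise of a controlled durability estimate. What stands is that, on the other meaning, none is planned.

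**Conclusion.** The point holds as a gap in specification with a modest, concrete remedy; it should be fixed. The start visit and the score are open, and the paired test has no protection against a period effect if the sequences are unequal (0.90t instead of t at 4:6 with P = 0.5t). The choice of start can move the estimate from t to 0.75t at 1:1 and L = 0.5 with a stable residue. Under fading or limited further gain it moves it between 0.875t and 1.125t. All of these sizes rest on assumed inputs on the raw-change scale; the direction and size on the SAP's normalised scale are not established. Separately, followed as written, the plan yields no controlled estimate of benefit that outlasts treatment, although a randomised comparison is available at the end of wash-out.

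**What to change.** 1. Define each arm's change from its own pre-arm assessment: the last Phase I assessment of that outcome for arm 1, and the end of wash-out for arm 2. State whether on- or off-stimulation scores are used. Show the study-baseline version as a sensitivity analysis.
2. Replace the plain paired t-test with its period-adjusted form: average the two sequences' mean differences with equal weight and use the within-sequence variance. This costs one degree of freedom. With an assumed effect of 1 SD of the paired difference at 5:5, power is about 79% instead of 80% when there is no period effect. It removes the period term, not carry-over bias.
3. For each outcome collected at the end of wash-out, report the baseline-adjusted B-first versus A-first difference with a 95% CI. It is a descriptive estimate, not a carry-over pre-test that decides the main analysis. It will be imprecise, as the half-widths above show. Which outcomes it can cover depends on the design figure, which is not shown here. The timeline note says that in weeks without an asterisk "only GRASSP quantitative prehension and grip & pinch strength measurements will be done", so those measures at least appear to be available.
4. State that before-after change in Phase III does not separate stimulation from therapy alone, because by then every patient is to have had both.

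No new visits are needed. The cost is SAP wording, the small loss of power in item 2, and one added descriptive analysis.
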